8.2 SAFETY ASSESSMENTS

We will continue to track patient safety data as usual for all patients in the epilepsy monitoring unit. We maintain an electronic database in which we record complications. We will report any new information or safety events per Mount Sinai IRB.

To protect participants against fatigue, frequent breaks will be offered during every session. Research sessions will be immediately interrupted for any health-care-related needs. Involved physician and nursing personnel, as well as the research team will carefully attend to the comfort of every participant. Participants will be made aware of their right to discontinue a session at any time, without repercussion.

Provisions for Research Related Harm or Injury: The subject should promptly tell the person in charge of the research if they believe that they have been injured because of taking part in this study. If a subject is injured as a result of study participation, Mount Sinai will provide necessary medical treatment. Depending on the circumstances, the costs of the treatment may be covered by Mount Sinai Health System or may be billed to the insurance company just like other medical costs. Mount Sinai does not normally provide any other form of compensation for injury.

8.3 ADVERSE EVENTS AND SERIOUS ADVERSE EVENTS

8.3.1 DEFINITION OF ADVERSE EVENTS

An adverse event (AE) is any untoward medical occurrence in a subject during participation in the clinical study or with use of the experimental agent being studied. An adverse finding can include a sign, symptom, abnormal assessment (laboratory test value, vital signs, electrocardiogram finding, etc.), or any combination of these.

A serious adverse event (SAE) is any adverse event that results in one or more of the following outcomes:

- Death
- A life-threatening event
- Inpatient hospitalization or prolongation of existing hospitalization
- A persistent or significant disability/incapacity
- An important medical event based upon appropriate medical judgment

CLASSIFICATION OF AE SEVERITY

AEs will be labeled according to severity, which is based on their impact on the patient, using a 1-4 scale. An AE will be termed “mild” (1) if it does not have a major impact on the patient, “moderate” (2) if it causes the patient some minor inconvenience, “severe” (3) if it causes a substantial disruption to the patient’s well-being and “life-threatening” (4) if it causes complications that can result in death.

8.3.1.1 RELATIONSHIP TO STUDY INTERVENTION/EXPERIMENTAL MANIPULATION

AEs will be categorized according to the likelihood that they are related to the study intervention using a 0-5 scale. Specifically, they will be labeled definitely unrelated (0), unlikely (1), potentially related (2), probably related (3) or definitely related (4) to the study intervention.

- Definitely Unrelated (0) – The AE is completely independent of study procedures administration, and/or evidence exists that the event is definitely related to another etiology.
- Unlikely to be related (1) – A clinical event, including an abnormal laboratory test result, whose temporal relationship to study procedures administration makes a causal relationship improbable (e.g., the event did not occur within a reasonable time after administration of the study procedures) and in which other drugs or chemicals or underlying disease provides plausible explanations (e.g., the participant’s clinical condition, other concomitant treatments).

- Potentially Related (2) – There is some evidence to suggest a causal relationship (e.g., the event occurred within a reasonable time after administration of study procedures). However, other factors may have contributed to the event (e.g., the participant's clinical condition, other concomitant events). Although an AE may rate only as “possibly related” soon after discovery, it can be flagged as requiring more information and later be upgraded to “probably related” or “definitely related”, as appropriate.
- Probably Related (3) – There is evidence to suggest a causal relationship, and the influence of other factors is unlikely. The clinical event, including an abnormal laboratory test result, occurs within a reasonable time after administration of the study procedures, is unlikely to be attributed to concurrent disease or other drugs or chemicals, and follows a clinically reasonable response on withdrawal.
- Definitely Related (4) – There is clear evidence to suggest a causal relationship, and other possible contributing factors can be ruled out. The clinical event, including an abnormal laboratory test result, occurs in a plausible time relationship to study procedures administration and cannot be explained by concurrent disease or other drugs or chemicals. The response to withdrawal of the study procedures should be clinically plausible. The event must be pharmacologically or phenomenologically definitive.

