2.3 RISK/BENEFIT ASSESSMENT

2.3.1 KNOWN POTENTIAL RISKS

EMU patients will be under standard neurology and nursing care with video/medical monitoring in the EMU. Note that these patients typically have their medications tapered during their stay in order for them to have seizures, which is the goal of the clinical monitoring. In the event of a seizure, standard protocols will be followed on the unit. Again, patients are supposed to have multiple seizures during this stay in the EMU. A member of the study team will always be present during the testing required for this study, including testing that involves stimulation.

- Cognitive testing: all cognitive and memory tests are designed to be minimally difficult. Some subjects may find the tests to be stressful, tiring, or boring. Cognitive testing will not interfere with their epilepsy monitoring or treatment. Standard medical care and safety protocols during EMU admission will not be altered by participation in this study. If an intervention is medically required due to the occurrence of seizures or post-ictal complications (including but not limited to the administration of sedating or anticonvulsant medications, resuscitative measures including supplemental oxygen, or patient restraint for safety in the setting of post-ictal agitation), the cognitive testing will be aborted and/or deferred until a time when the patient's medical condition permits continuation of the testing. Procedures to mitigate risks of cognitive testing: session times will be minimized, and assessments may take place over more than once session, if needed and appropriate. Participants may also take breaks, as needed. Subjects have the right to refuse to answer questions they feel are too distressing, as well as to terminate any one part or the whole of their participation at any time.

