- Single neuron recordings: we will use augmented macro-micro electrodes that include, in addition to the macro contact sites routinely used for clinical recordings, micro contact filaments to allow electrophysiological recordings that can isolate individual neurons. There is no additional risk of intracerebral hemorrhage or tissue injury compared with the standard clinical macro electrodes. There are no reports of any ill effects from these FDA-approved electrodes for clinical EEG recording. Recordings from the microelectrode filaments that protrude from the macro electrode shaft do not interfere with the usual clinical recordings and have the potential to significantly improve some aspects of mapping seizures and cognition. Every study examining the design and safety of such micro-macro depth electrodes has found them to be as safe and effective as standard depth electrodes for intracranial monitoring (House 2006, Van Gompel 2008, Waziri 2009, Hefft 2013, Misra 2014, Carlson 2018). Their use requires no extra surgical procedures. Procedures to mitigate risks of single neuron recording: we will only use single-unit recording electrodes in locations targeted for clinical reasons. The locations and number of sEEG electrodes will therefore be based on clinical necessity and will not be changed due to participation in this study. Only a subset of sEEG electrodes (typically 1-4) will be replaced by macro-micro electrodes.
- Brain stimulation: we do not anticipate any significant increase in risk, since we will be using FDA-approved electrodes and stimulating according to clinical protocols. Stimulation will be carried out using macro electrodes only, even if the patient consented to microelectrode implantation. It is possible that brain stimulation could produce a seizure that causes injury. We will monitor the occurrence of seizures producing injury in all enrolled patients. Patient safety will be tracked by the PI and research staff in real time and reported to the Mount Sinai IRB according to the guidelines in HRP-214. Procedures to mitigate stimulation testing risks: to minimize the risk of triggering a seizure through stimulation, we will limit stimulation to levels routinely used by the clinical team for functional mapping (≤ 6 mA). Stimulation testing will only be carried out once the patient has been cleared

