8.3.3 ADVERSE EVENT REPORTING

The PI will monitor the study for any AEs, although we do not anticipate any given the nature of the study. Adverse events will be documented by the research team and reported to the IRB using IRB communication channels. If action is deemed appropriate to ensure patient safety by the IRB following AE review, the research team will implement these changes in all future participants. In addition, if necessary (i.e. multiple AEs are reported) the PI and the research team will maintain a log of all AEs.

SAEs that are unanticipated, serious, and possibly related to the study intervention will be reported to the Independent Monitor and IRB in accordance with requirements.

- Unexpected fatal or life-threatening AEs related to the intervention will be reported within 7 days. Other serious and unexpected AEs related to the intervention will be reported within 15 days.
- Unrelated SAEs will be handled in a less urgent manner but will be reported to the Independent Monitor, IRB and other oversight organizations in accordance with their requirements.

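### The drug-style causality criteria in section 8.3.1.1 bias stimulation-evoked seizures and their injuries toward grade 2, and the reporting limits do not say whether grade 2 counts as related

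*Combined protocol and SAP*

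**What the plan says.** **Causality scale (8.3.1.1).** Grade 3 opens with "There is evidence to suggest a causal relationship, and the influence of other factors is unlikely". It then asks for reasonable timing, and that the event "is unlikely to be attributed to concurrent disease or other drugs or chemicals, and follows a clinically reasonable response on withdrawal". Grade 4 asks that other contributing factors be excluded and that the event "occurs in a plausible time relationship to study procedures administration and cannot be explained by concurrent disease or other drugs or chemicals". It adds "The response to withdrawal of the study procedures should be clinically plausible", and that the event be definitive on pharmacological or phenomenological grounds. Grade 2 covers events with some evidence of causation to which other factors may have contributed, and gives the participant's clinical condition as an example. A grade 2 event may be upgraded when more is known.

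**Named harm and setting (2.3.1).** On stimulation the protocol states: "It is possible that brain stimulation could produce a seizure that causes injury". On the monitoring stay it states that medications are typically tapered and that "patients are supposed to have multiple seizures during this stay in the EMU". Section 5.1 limits enrolment to drug-resistant epilepsy.

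**Reporting (8.3.3, repeated in 10.1.9).** The lead sentence covers unanticipated serious events that are *possibly* related. The limits below it drop that qualifier: "Unexpected fatal or life-threatening AEs related to the intervention will be reported within 7 days", and a 15-day limit is worded in the same way. Neither section ties *related* to a grade.

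**The concern.** The criteria read as if carried over from a drug trial. They ask what happened when exposure was withdrawn, and whether disease or other drugs could explain the event. In this study the exposure is a brief current, and the disease under treatment produces the same event as the main named harm.

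The grade matters because little else in the plan separates research harm from expected seizures. There is no randomization or blinding (6.3), and no safety analysis is planned (9.4.5). Section 4.1 says that research stimulation will run longer than clinical mapping, and sometimes at other sites, so attribution is a real question. If clearly evoked events settle at grade 2, the record cannot tell them from events that merely happened nearby in time. A grade 2 label also leaves it uncertain whether the 7- and 15-day limits apply.

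**Working it through.** No arithmetic bears on the main point. The check sets each criterion beside two events: (A) a seizure that starts during stimulation, and (B) a fixed injury caused by that seizure.

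**Grade 4**
- *Timing:* A and B can meet it.
- *Not explicable by concurrent disease, other factors excluded:* read literally, A all but fails. Every participant has epilepsy, and epilepsy can explain a seizure. B inherits the failure, because its cause is the seizure.
- *Response to withdrawal:* softer, since it says *should be*. A seizure that ends and does not recur once stimulation stops could satisfy it. B shows no such response.
- *Definitive event:* A can meet the phenomenological option. This is a further requirement on top of the concurrent-disease test, so it does not replace that test.

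**Grade 3**
- *Timing:* A and B can meet it.
- *Unlikely to be due to concurrent disease:* a matter of judgement. A can meet it when onset is tightly linked to stimulation.
- *Response on withdrawal:* joined to the other tests by *and*. A is arguable, as under grade 4. B fails if the words are applied as written, because an injury does not resolve when a current stops.
- The protocol does not say what withdrawal means for a brief stimulus. The sections that might define it, 6.1.1 and 7.1, are marked not applicable.

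**Grade 2**
- A and B always fit. The grade's example of another contributing factor, the participant's clinical condition, describes everyone enrolled.
- The upgrade route does not help by itself, because the event must still meet the definition of the higher grade.

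The documents give no rule for telling an evoked from a spontaneous seizure, so nothing offsets this downward pull.

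**From grade to reporting**
- The lead sentence in 8.3.3 and 10.1.9 says *possibly related*; the 7- and 15-day limits say *related*; the contrasting item says *unrelated*.
- Grade 2 is labelled *potentially related*, but its own definition also calls it *possibly related*. It can be read as inside or outside the limits.

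**The scale itself**
- Section 8.3.1.1 announces a 0–5 scale, which has 5 − 0 + 1 = 6 levels. It defines 0, 1, 2, 3 and 4, which is 5 levels.

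**The case against.** The strongest reply is that this is awkward wording which competent assessors will read sensibly. Relatedness is judged only by staff trained and authorised to diagnose (8.3.2). A study team member is present during stimulation, and the patient is on iEEG and video. Grade 3 asks only that other causes be unlikely. This stands: grade 3 remains reachable for an evoked seizure, and the defect is a bias rather than a bar.

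The safeguards also stand. All adverse events are documented whatever their cause (8.3.2). The evaluation of serious events is due within 10 working days whatever the grade (8.3.4). The independent monitor reviews any adverse event (10.1.6), and section 2.3.1 commits to tracking seizures that cause injury.

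On reporting, 10.1.9 ends its lead sentence with a colon, so the limits can be read as elaborating *possibly related*, with grade 2 inside. That is the more natural reading, but it is not stated. The limits also apply only to unexpected events, and a harm already named in 2.3.1 may count as expected, so the ambiguity affects fewer events than it first appears.

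Section 2.3.1 places research stimulation after clearance for explantation. The documents do not give medication status at that point, so the taper is weaker background than it looks. The underlying epilepsy remains a competing explanation.

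A reader might infer that evoked harms can never be graded 3 or 4, so that the study would record no related events and appear falsely safe. The documents do not support that. Grade 3 is open to judgement, events held at grade 2 still appear as potentially related, and no planned analysis counts grades. Nor do the criteria fail for every named harm: stress or tiredness from testing (2.3.1) can resolve when testing stops.

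**Conclusion.** The point holds as a bias in attribution. Read literally, 8.3.1.1 nearly closes grade 4 to a stimulation-evoked seizure and applies to grade 3 a withdrawal test that has no meaning for a fixed injury. Both push such events toward grade 2 even when the link to stimulation is clear. Events are still captured and reviewed; what suffers is the stated cause and, for unexpected serious events, certainty about the 7- and 15-day limits.

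The size cannot be calculated. The documents state neither how many participants will be stimulated nor how often a seizure or injury is expected. The conclusion assumes that assessors apply the definitions as written; a lenient assessor would reduce the bias but make grading inconsistent between assessors. The change is worth making because it is cheap and the grade is the protocol's main device for attributing harm.

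**What to change.** In 8.3.1.1:
- Apply the response-on-withdrawal test only where a response can be observed, and not to one-off or irreversible events.
- State that underlying epilepsy alone does not bar grades 3 or 4 when the assessor judges stimulation the more likely cause, from timing relative to stimulation and the concurrent iEEG and video.
- Reconcile the 0–5 range with the five grades defined, and choose one of *potentially* and *possibly* related.

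In 8.3.3 and 10.1.9, use one term throughout and state that grades 2 to 4 count as related for the 7- and 15-day limits.

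The cost is a wording amendment. It needs no new data, because the recordings are already made, and it leaves stimulation and clinical care unchanged. The downside is that some events will be graded as more related, or reported sooner, than under the present text.

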8.3.2 TIME PERIOD AND FREQUENCY FOR EVENT ASSESSMENT AND FOLLOW-UP

The occurrence of an adverse event (AE) or serious adverse event (SAE) may come to the attention of study personnel during study visits and interviews of a study participant presenting for medical care, or upon review by a study monitor. All AEs, not otherwise precluded per the protocol, will be captured on the appropriate case report form (CRF). Information to be collected includes event description, time of onset, clinician's assessment of severity, relationship to study procedures (assessed only by those with the training and authority to make a diagnosis), and time of resolution/stabilization of the event. All AEs occurring while on study will be documented appropriately regardless of relationship. All AEs will be followed to adequate resolution.

Any medical or psychiatric condition that is present at the time that the participant is screened will be considered as baseline and not reported as an AE. However, if the study participant's condition deteriorates at any time during the study, it will be recorded as an AE. Changes in the severity of an AE will be documented to allow an assessment of the duration of the event at each level of severity to be performed. Documentation of onset and duration of each episode will be maintained for AEs characterized as intermittent.

The PI's team will record events with start dates occurring any time after informed consent is obtained until the last day of participation in the hospital stay portion of the study. Events will be followed for outcome information until resolution or stabilization.

8.3.3 ADVERSE EVENT REPORTING

The PI will monitor the study for any AEs, although we do not anticipate any given the nature of the study. Adverse events will be documented by the research team and reported to the IRB using IRB communication channels. If action is deemed appropriate to ensure patient safety by the IRB following AE review, the research team will implement these changes in all future participants. In addition, if necessary (i.e. multiple AEs are reported) the PI and the research team will maintain a log of all AEs.

SAEs that are unanticipated, serious, and possibly related to the study intervention will be reported to the Independent Monitor and IRB in accordance with requirements.

- Unexpected fatal or life-threatening AEs related to the intervention will be reported within 7 days. Other serious and unexpected AEs related to the intervention will be reported within 15 days.
- Unrelated SAEs will be handled in a less urgent manner but will be reported to the Independent Monitor, IRB and other oversight organizations in accordance with their requirements.

8.3.4 SERIOUS ADVERSE EVENT REPORTING

In consultation with the PI, a trained member of the study team will be responsible for conducting an evaluation of a serious adverse event and shall report the results of such evaluation to the NIH and the reviewing Institutional Review Board (IRB) as soon as possible, but in no event later than 10 working days after the investigator first learns of the event.

DESIGNATION OF AN INDEPENDENT MONITOR

The Independent Monitor for this study is [name] (Dept. of Neurology, Icahn School of Medicine). [name] is not associated with this research project and thus works independently of the study team. [name] is not a part of the key personnel involved in this project, and is qualified to review the patient safety data generated by this study because of her expertise in Neurology.

8.3.5 REPORTING EVENTS TO PARTICIPANTS

N/A.

8.3.6 EVENTS OF SPECIAL INTEREST

N/A.

8.3.7 REPORTING OF PREGNANCY

N/A - pregnant women are excluded from the study.

9 STATISTICAL CONSIDERATIONS

9.1 STATISTICAL HYPOTHESES

Primary endpoints: Investigate the neurophysiological correlates of human cognitive processes. We hypothesize that modulations in neural activity, as recorded by electrophysiological or electrochemical techniques, will be associated with different cognitive aspects of the behavioral tasks that the patients will complete. Specifically, we expect that cognitive brain functions will localize to a variety of brain areas, including temporal and prefrontal regions, with electrophysiologic signatures in the theta (4-8Hz) and high-gamma (70-200 Hz) frequency ranges. Scientists have theorized that cyclic changes in the brain's electrical activity (brain oscillations) play a fundamental role in memory function. Studies have focused on the theta (slow) rhythm which oscillates in the 4-8Hz frequency range and high gamma activity which appears in the 70 to 200 Hz frequency range because these neural signatures appear prominently during a wide range of cognitive tasks and are hypothesized to be the cause of all neural activity - our thoughts, feelings and perceptions. The relationship between brain oscillations and neuronal activity is largely unexplained so our study aims to investigate the correlation between brain oscillations and the neuronal activity of

human cognition. We will also investigate the contribution and information processing capabilities of individual neurons.

Secondary endpoints: investigate the causal involvement of individual brain areas in cognitive processes through targeted electrical stimulation. We hypothesize that modulation of brain electrical activity through targeted stimulation will reversibly affect patient behavior. Specifically, we expect that stimulation of prefrontal cortical areas (i.e. orbitofrontal cortex) will result in changes in associated behavior (for example, in choices during decision-making behavior) that will be sampled through behavioral tasks.

Tertiary endpoints: characterize the genetic and molecular composition of human brain tissue to reveal important information about genetic differences in epileptic tissue and correlate electrophysiological and molecular biological measures to brain function and clinical diagnoses. We hypothesize that there will be significant association between expression of individual genes (e.g. related to synaptic function such as neurotransmitter receptors, voltage-gated ion channels, GPCRs) and (1) clinical diagnosis (e.g. epilepsy type, psychiatric comorbidities) and (2) neurophysiological activity (e.g. theta [4-8Hz] or high-gamma [70-200 Hz] frequency power, oscillatory coherence, etc.) as recorded in the deep temporal lobe area prior to resection.

